9.4. Outcome Measures

In this research protocol the dependent variables will be treatment adherence and gross motor function as primary outcome measures and quality of life as a secondary measure, while the independent variable is the type of physiotherapy program received either the play therapy-based physiotherapy program or the conventional physiotherapy program.

9.4.1. Treatment Adherence

Treatment adherence will be measured as a primary outcome and refers to the extent to which a patient follows or complies with the recommended or prescribed treatment plan and it's a process in which the appropriate treatment is decided after a proper discussion with the patient and its family to establish its goals and motivations (B). Having into account this definition, treatment adherence will be measured using objective and subjective measures noted in a logbook by the physiotherapist after each session ([Annex IV](#)). In this logbook it will be measured the percentage of completed physiotherapy sessions out of the total number of sessions scheduled, the percentage of exercises done in each session, how the child felt while doing each exercise and if parents/carers have followed the recommendations given. The maximum punctuation is 12 and the minimum is 1 point. The physiotherapist will not know which punctuation receive each option in order to reduce the risk of bias.

In addition, the Goal Attainment Scale (GAS) will be used as a method to measure if the goals determined before starting the intervention has been achieved or not (B), which is highly related to treatment adherence. This goal setting will be done based on parents or guardians and children's needs and motivations, which will be commented with the physiotherapist so that he or she can plan a tailored physiotherapy program. Moreover, all the goals will follow the SMART criteria to try to be as much objective and measurable as possible.

B. Cusick A, et al. A comparison of goal attainment scaling and the Canadian Occupational Performance Measure for paediatric rehabilitation research. *Pediatr Rehabil.* 2006 Jun;9(2):149-57.

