15.4. Annex IV: Logbook

Patient nº						
Data						
Session nº						
Assistance	 Yes					0p
	 No					1p
Time of session done	 0-15 minutes					1p
	 15-30 minutes					2p
	 30-45 minutes					3p
Exercises	1	2	3	4		
Task completion	 Not done	 Not done	 Not done	 Not done	0p	
	 Initiates	 Initiates	 Initiates	 Initiates	1p	
	 Partially complete	 Partially complete	 Partially complete	 Partially complete	2p	
	 Completes	 Completes	 Completes	 Completes	3p	
Did you help him/her?	 Yes	 Yes	 Yes	 Yes	1p	
	 No	 No	 No	 No	0p	
Did he/she laugh?	 Yes	 Yes	 Yes	 Yes	1p	
	 No	 No	 No	 No	0p	
Did he/she cry?	 Yes	 Yes	 Yes	 Yes	0p	
	 No	 No	 No	 No	1p	
Did he/she get mad?	 Yes	 Yes	 Yes	 Yes	0p	
	 No	 No	 No	 No	1p	
Did the parents follow the recommendations?	 Yes				1p	
	 No				0p	
TOTAL SCORE					  / 12	

This is the logbook that will be used during the treatment adherence measurement, but the physiotherapist will not have the punctuation in order to not bias him or her.

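### The Annex IV logbook gives the attendance point for missing a session, and the stated range of 1 to 12 does not match the form as keyed

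*Protocol*

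**What the plan says.** Section 9.4 states that "the dependent variables will be treatment adherence and gross motor function as primary outcome measures". Section 9.4.1 says the logbook is to record, among other things, "the percentage of completed physiotherapy sessions out of the total number of sessions scheduled", and gives the score range: "The maximum punctuation is 12 and the minimum is 1 point".

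Annex IV holds the form and its points, and says of it: "This is the logbook that will be used during the treatment adherence measurement". The rows are:

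- Attendance, whose first line reads "Assistance Yes 0p"; the No box carries 1 point.
- "Time of session done": 1, 2 or 3 points, with no zero option.
- "Task completion": 0 to 3 points, in each of four exercise columns.
- Helped, laughed, did not cry, did not get mad: 1 point each, again in each of the four columns.
- "Did the parents follow the recommendations": 0 or 1 point, once per session.
- A total out of 12.

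Neither place says whether the four exercise columns are summed, averaged or reduced to one, or how a missed session is scored. Section 9.6 adds that each part of the logbook will also be analysed separately when predictors of adherence are sought.

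**The concern.** An adherence score should rise when the child attends. Here the attendance row gives its only point for not attending. The row has to mean attendance: it comes first, section 9.4.1 says completed sessions are captured, and helping the child has a row of its own. If it meant help, it would contradict that row and the form would not score attendance at all.

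The physiotherapist does not see the points, so the person filling in the form cannot notice the reversal. The item enters the total of a primary-outcome measure, and it would also be analysed alone, where any predictor of attendance would appear with the wrong sign. Separately, because no column rule is given and the stated range fits no attended session, two analysts following the protocol could produce totals on different scales.

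**Working it through.** **Inputs.** All points come from the Annex IV key. One exercise column is worth 0 to 3+1+1+1+1 = 7. Section 9.3 schedules 32 sessions per child.

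**The plan's own figure.** Taking each row once and ignoring whether the answers can occur together:

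- sum of row maxima: 1+3+3+1+1+1+1+1 = 12
- sum of row minima: 0+1+0+0+0+0+0+0 = 1

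This reproduces 12 and 1, and is probably how they arose. Under the printed key, however, the 12 needs the point for absence together with a 30-45 minute session, which cannot both occur.

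**Range for an attended session** (attendance + time + exercises + parents):

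| Key | Exercise rule | Minimum | Maximum |
|---|---|---|---|
| Printed (attended = 0) | one column, or mean of four | 0+1+0+0 = 1 | 0+3+7+1 = 11 |
| Printed | four columns summed | 0+1+0+0 = 1 | 0+3+28+1 = 32 |
| Rekeyed (attended = 1) | one column, or mean of four | 1+1+0+0 = 2 | 1+3+7+1 = 12 |
| Rekeyed | four columns summed | 1+1+0+0 = 2 | 1+3+28+1 = 33 |

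The stated maximum is met only in the third line, and there the stated minimum of 1 no longer holds for an attended session.

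**Missed session.** Scored only on the attendance item, it gets 1 point as printed (2 with the parents' point). The worst attended session also scores 1. Rekeyed, the missed session gets 0 (1 with the parents' point).

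**Attendance item alone over 32 sessions.** Printed: 32 × (1 − a), where a is the proportion attended. Rekeyed: 32 × a.

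- a = 1: 0 printed, 32 rekeyed
- a = 0.75: 8 printed, 24 rekeyed
- a = 0.5: 16 printed, 16 rekeyed

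**Effect on the arm difference, if missed sessions are scored.** Let D be the difference between arms in proportion attended, S the other points on an attended session and M the other points on a missed one, with S and M equal in both arms.

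- Rekeyed difference in mean score per scheduled session: D × (S + 1 − M)
- Printed difference: D × (S − 1 − M)
- Loss: 2D

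Illustration with assumed values (attendance 90% versus 70%, so D = 0.2, and S = 8):

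- M = 0: 0.2 × 9 = 1.8 rekeyed, 0.2 × 7 = 1.4 printed
- M = 3: 0.2 × 6 = 1.2 rekeyed, 0.2 × 4 = 0.8 printed

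The loss is 0.4 points in both cases. With D = 0.1 it would be 0.2. With M = 0 the printed difference cannot change sign, because S is at least 1.

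**The case against.** The strongest reply is that the reversed key may never affect the comparison. Sections 9.4.1 and 9.5 have the logbook completed after each session. If only sessions that took place are logged, the attendance item is 0 for everyone and adds no difference between arms. This stands as a limit on the size of the harm. It does not make the key right, since the item would then carry no information about the attendance it is meant to record.

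Attendance rate is also listed as a variable of its own in section 9.6 and Annex V, and the ticked boxes could be rescored later. Both are true, but neither corrects the logbook total as specified. The table was read from a PDF, so the order of 0 and 1 should be checked against the original. The neighbouring rows read coherently, so a swap is unlikely; if there was one, the summed maximum would be 33, still not 12, although 12 would hold for one column or the mean.

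A reader might infer more than the documents support:

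- *That the four-exercise form cannot produce 12.* It can, since the summed range runs from 1 to 32. Twelve is just not its maximum.
- *That the stated 12 proves the key is reversed.* Row maxima add to 12 whichever way attendance is keyed. The case rests on what the item means.
- *That the better-attending arm would score lower overall.* One item is reversed. In the illustration the total is attenuated, and the 90% arm still leads.
- *That an absent child scores 4 against 1 for a child who attends and refuses.* This requires someone to tick the shortest time band and the no-crying and no-anger boxes for exercises that never took place. On the attendance item alone the two tie at 1.
- *That the loss can be set against the 1.2 in Annex I.* Nothing links that figure to the logbook scale.
- *That the help item is also reversed.* On the one-column count, unaided completion reaches 10 and helped completion 11, but nothing in the protocol says that needing help means poorer adherence. This is a question for the authors.

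**Conclusion.** The point holds as a scoring error in a measure of a primary outcome. On the printed key, attendance earns nothing and absence earns a point, and an attended session has a maximum of 11 or 32 depending on an unstated column rule, never 12. These statements follow from the form alone, subject to the key having been read correctly.

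The effect on the treatment comparison is conditional. If missed sessions are scored, the arm difference in mean score per scheduled session shrinks by twice the difference in attendance proportions, and the separate analysis of the attendance item has the wrong sign. If missed sessions are not logged, the item is constant and the comparison is unaffected by it. The protocol gives no expected attendance, so the 0.4-point figure is illustrative only. The correction belongs before the form is first used.

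**What to change.** After checking the printed points against the original form:

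1. In Annex IV, set Assistance to Yes = 1 and No = 0.
2. State that missed scheduled sessions are logged and score 0 on the attendance, time and exercise items. Add a zero-minutes option worth 0 points, leave the crying and anger items unscored for such sessions, and say whether the parents' item still counts.
3. State that the exercise items are averaged over the exercises planned, giving 0 to 7, so that the maximum is 1+3+7+1 = 12.
4. Correct the range in section 9.4.1 to 0 to 12. A missed session then scores 0 (1 if the parents' point is kept), and the lowest attended session scores 2.
5. Have the authors confirm whether a point for being helped is intended.

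The cost is a one-page change to the form and a sentence in section 9.4.1. No new data are needed, and the Annex I calculation does not depend on it.

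### The adherence logbook has no zero score for a missed session, so an absence can score above a poor attended session

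*Protocol*

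**What the plan says.** Section 9.4.1 of the Protocol gives the logbook its weight: "Treatment adherence will be measured as a primary outcome". It says the logbook is to capture, among other things, "the percentage of completed physiotherapy sessions out of the total number of sessions scheduled". It then fixes the range of the score: "The maximum punctuation is 12 and the minimum is 1 point".

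Annex IV prints the form and its points. The first item, labelled Assistance, is read here as attendance, because help from the physiotherapist is asked separately ("Did you help him/her"). As printed, Yes gives 0 points and No gives 1. The time item has three bands worth 1, 2 and 3 points, and the lowest starts at zero minutes. For each of four exercises the form then asks about "Task completion" (0 to 3 points), help (Yes 1), "Did he/she laugh" (Yes 1), crying (No 1) and "Did he/she get mad" (No 1). The last item is "Did the parents follow the recommendations" (Yes 1). The total is out of 12.

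No item has a not-applicable option, and there is no instruction for the remaining items when the attendance answer is No. Sections 9.4.1 and 9.5 have the physiotherapist fill in the logbook after each session. The physiotherapist does not see the points.

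**The concern.** The form foresees non-attendance, since it has a box for it, but its key is written as if every session took place. A child who stayed away did not cry and did not get angry, so a physiotherapist who completes every line would truthfully tick two answers that each earn a point. The time item offers nothing below 1 point. A missed session is the plainest form of non-adherence, yet it can collect points and can even score above a session that the child attended in distress.

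At stake is the meaning of one measure of a primary outcome. Points credited for absences pull the arms' mean logbook scores together wherever the arms differ in attendance. If the physiotherapists complete the form differently for absent children, the score also picks up differences between them that have nothing to do with the child.

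**Working it through.** **Inputs.** All item scores come from Annex IV and the stated range from section 9.4.1. Exercise items are counted once (or averaged over the four exercises).

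| Item | Lowest | Highest | Absent, all items ticked, parent item No | Worst attended session |
|---|---|---|---|---|
| Assistance, as printed (Yes 0, No 1) | 0 | 1 | 1 | 0 |
| Time | 1 | 3 | 1 | 1 |
| Task completion | 0 | 3 | 0 | 0 |
| Help | 0 | 1 | 0 | 0 |
| Laughing | 0 | 1 | 0 | 0 |
| Crying (No = 1) | 0 | 1 | 1 | 0 |
| Anger (No = 1) | 0 | 1 | 1 | 0 |
| Parents | 0 | 1 | 0 | 0 |
| **Total** | **1** | **12** | **4** | **1** |

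**Step 1: the stated range.** The sums of lowest and highest points are 1 and 12, which matches section 9.4.1. Summing the four exercise columns would give a maximum of 1 + 3 + 4 × 7 + 1 = 33, which conflicts with the printed total of 12, so that reading is not used. The floor of 1 comes from the time item alone.

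**Step 2: what a missed session can score as printed.**
- Only attendance ticked: 1.
- Attendance and time: 1 + 1 = 2.
- Attendance, time, no crying, no anger: 1 + 1 + 1 + 1 = 4.
- The same with the parent item Yes: 5.

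The range is 1 to 5.

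**Step 3: the same with attendance re-keyed (Yes 1, No 0).** Each total falls by 1, so the range is 0 to 4. Zero is reached only if every other scoring item is left blank.

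**Step 4: comparison with the worst attended session.** This is a session of up to 15 minutes with no task done, no help, no laughing, crying, anger, and the parent item No. As printed it scores 0 + 1 = 1, and re-keyed 1 + 1 = 2. The fully ticked absence with the parent item No scores 4 and 3 respectively, so it ranks higher under either key.

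**Step 5: size in an assumed example.** The documents give no expected attendance or mean score. Assume attended sessions average A = 9 points, attendance is 90% in one arm and 75% in the other, attendance is re-keyed, and a child's score is the mean over scheduled sessions. With m points per missed session, the attendance-driven difference is (0.90 − 0.75) × (A − m), and the fraction lost is m/A.

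| m | Difference | Lost |
|---|---|---|
| 0 (other items blank) | 0.15 × 9 = 1.35 | 0% |
| 1 (time only) | 0.15 × 8 = 1.20 | 11% |
| 3 (time, crying, anger) | 0.15 × 6 = 0.90 | 33% |
| 4 (and parent item Yes) | 0.15 × 5 = 0.75 | 44% |

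**The case against.** The strongest reply is that nobody would score the mood of an absent child. Section 9.4.1 ties those items to how the child felt while exercising, and the logbook is filled in after a session. The natural course is to tick No for attendance and leave the rest blank, which gives 0 once the attendance key is corrected. This stands as far as it goes, and it is why the range starts at 0%. But no rule says so. Table 3 budgets for four physiotherapists, who do not see the points and so cannot know that a No earns credit. As printed, even the blank form scores 1. If instead no form is completed for a missed session, the attendance No box has no use and absences drop out of the score altogether.

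A second reply is that the stated minimum of 1 is only the arithmetic floor of the form. That is right: it does not show that an absence receives 3 or 4 points. It does exclude zero. With attendance re-keyed, an attended session cannot fall below 2, so a score of 1 could then belong only to an absence.

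A third reply is that attendance rate is summarised as its own variable (section 9.6 and Annex V). This also stands: the attendance information is not lost to the trial.

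Finally, section 9.7 promises instructions on completing the logbook, and these could contain a missed-session rule. They would not change the range printed in section 9.4.1.

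Two stronger readings are tempting. One is that every missed session is credited with 3 points and a third of the effect is lost. The documents do not support this: the credit depends on how the form is filled in, and the 33% is one point in an assumed range. The other is that mood points should also be withheld when an attended exercise is marked as not done. Section 9.4.1 wants the child's feelings recorded, and a calm child who does not perform differs from one who refuses in distress. That scoring is a matter of judgement, not an error.

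**Conclusion.** The point holds for the logbook total. The printed key and the stated minimum leave no zero for a missed session, although the form expects missed sessions to be entered. An absence can score 1 to 5 as printed and 0 to 4 with attendance re-keyed. When all applicable items are ticked and the parent item is No, it outranks the worst attended session, by 4 to 1 as printed and by 3 to 2 re-keyed.

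The 0% to 44% shrinkage rests on the assumed mean of 9, the assumed attendance of 90% and 75%, and the corrected key. It is in raw points. A fixed credit per absence also narrows the attendance-driven spread between children, so the loss in standardised effect or power would be smaller; it was not calculated. A reader might infer that the trial cannot detect an attendance difference at all. It can, through the separate attendance rate.

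**What to change.** State in Annex IV and section 9.4.1 that when the attendance answer is No, the session total is 0 and the time, exercise and mood items are not scored. The parent item may still be recorded and analysed on its own. Change the stated minimum from 1 to 0. Let each scheduled session enter the child's mean for as long as the child remains in the trial. Correct the reversed attendance key (Yes 1, No 0) in the same edit. An attended session can then reach 12; as printed it cannot exceed 11.

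The cost is a few lines of text before data collection starts, with no new data, visits or staff. The downside is small: mean logbook scores will be lower, and absences for reasons such as illness will also count as 0.

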Background: Children with cerebral palsy (CP) frequently struggle with gross motor function, which can interfere with their daily activities and quality of life. Although physiotherapy is an important intervention for improving gross motor function in children with cerebral palsy, adherence to treatment remains a challenge. Physiotherapy programs based on play therapy have been proposed as a new alternative approach to improving treatment adherence and gross motor function in children with cerebral palsy. The aim of this research protocol is to compare the efficacy of play therapy-based physiotherapy programs compared to traditional physiotherapy programs in improving treatment adherence and gross motor function in children with CP GMFCS level III-IV.

Methods: This study will be a randomized controlled trial with a sample size of 64 children aged 4-12 with CP GMFCS level III-IV. Participants will be randomly assigned to receive either a play therapy-based physiotherapy or conventional physiotherapy program 45 minutes twice a week for a period of 16 weeks. Treatment adherence will be measured using a combination of physiotherapy session attendance rates, an adherence logbook and the Goal Attainment Scale (GAS). Gross motor function will be assessed using the Gross Motor Function Measure (GMFM-88) and Quality of life will be measured using the CPQoL-Child, all this will be measured at baseline, 5 weeks, 10 weeks and 16 weeks of intervention and a follow-up at 24 weeks will be done. Data will be analysed using descriptive statistics, independent t-tests, ANCOVA and correlations.

Key words: infantile cerebral palsy, play-therapy, treatment adherence, gross motor function, quality of life and physiotherapy.

3. Título

La eficacia de los programas de fisioterapia basados en la terapia de juego frente a los programas de fisioterapia convencionales para mejorar la adherencia al tratamiento y la función motora gruesa en niños con parálisis cerebral GMFCS nivel III-IV: un protocolo de investigación para un ensayo controlado aleatorizado.

4. Resumen

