9.3. Intervention

The intervention will consist of two groups: a play therapy-based physiotherapy group (experimental group) and a conventional physiotherapy group (control group).

The play therapy-based physiotherapy group will receive 45 minutes sessions of play therapy-based physiotherapy twice a week for 16 weeks (32 sessions in total). The play therapy-based physiotherapy sessions will be conducted by a trained and licensed physiotherapist and will be planned incorporating playing activities such as ball games, obstacle courses, music, sensory toys, and pretend play combined with standard physiotherapy exercises ([Annex III](#)). All that, based on the child's interests and abilities, with the aim of engaging the child in a pleasant and enjoyable activity that simultaneously enhances gross motor function. Moreover, the physiotherapist will offer feedback and positive reinforcement throughout play therapy sessions to encourage adherence. The therapist will also give advice and assistance to the child as needed to ensure that they can do each exercise safely and efficiently and the family will receive home recommendations based on play to assist their worries and questions.

The conventional physiotherapy group will receive 45 minutes sessions of conventional physiotherapy twice a week for 16 weeks (32 sessions in total). The conventional physiotherapy sessions will also be conducted by a trained and licensed physiotherapist and will include standard physiotherapy exercises following the international clinical practice guideline from 2022 of Jackman M, et al (3). These sessions will be planned for each child's needs and goals, for improving gross motor function and increasing treatment adherence. Moreover, the physiotherapist will offer feedback and positive reinforcement throughout sessions to encourage adherence. The therapist will also give assistance as needed to ensure that they can do each exercise safely and efficiently and the family will receive home recommendations based on their worries and questions.

Both groups will get their respective treatments at the same location, and the study team will rigorously monitor adherence to the intervention program. The study team will also gather information on any adverse events or problems that may occur throughout the intervention.

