9.5. Data Collection

Many steps will be applied during the study to guarantee the security and confidentiality of participants' data. To begin, all data obtained will be kept totally secret and only authorized members of the study team will have access to it. To do the allocation concealment, a statistician will generate the randomization list by given to participants a unique identification number, which will be used to assign them to one or another group.

For the outcome measure assessment different procedures will be conducted. The GAS, the GMFM-88 and the CP QoL-Child will be done at baseline, after 5, 10 and 16 weeks and at the follow-up assessment at 24 weeks. In the baseline the GAS will be used as a way for the physiotherapist to plan the intervention and in the mid-term assessments the goals achievement will be measured, all this by the physiotherapist. The GMFM-88 will be assessed by the outcome assessor and the CP QoL-Child will be done by parents or caregivers who will give the questionnaire to the research assistants for them to score it and save it.

On the other hand, the logbook will be completed by the physiotherapist after each participant session and at the end of the 16 weeks intervention will be given to the research assistants to do the data collection and after that, the analysis.

All paper-based data will be stored in locked cabinets in a secure research facility and electronic data will be kept on a password-protected computer and will be stored and managed from Microsoft One Drive cloud, which contains a double security system. Exclusively authorized people will be able to access to the data.

Only de-identified data will be shared in any publications or presentations emerging from the study to protect the privacy and confidentiality of participants. Without express written authorization, participants' personal data will not be shared with anybody outside of the study team.

Once all the study is finished, the obtained data may be maintained for a limited time, as needed by institutional guidelines, before being securely deleted to prevent unauthorized access or use. Overall, the research team is committed to maintaining the greatest levels of privacy and confidentiality to protect the safety and well-being of all study participants.

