9.6. Data Analysis

All data collected from the assessments, questionnaires and the logbook will be analysed using appropriate statistical methods with the help of an expert statistician to achieve the aims of this research protocol. The statistical analyses will be conducted using a statistical software package such as JASP and the statistical significance will be set at p-value <0.05 and CI (Confidence Interval) 95%. When p-value $< 0,05$, the null hypothesis (H_0) will be rejected meaning that the results are statistically significant. The H_0 is: There is no significant difference between the effectiveness of play therapy-based physiotherapy programs and conventional physiotherapy programs in improving treatment adherence and gross motor function in children with cerebral palsy GMFCS level III-IV.

After collecting all data, it will be placed into a spreadsheet for basic data cleaning and categorization ([Annex V](#)). Descriptive statistics (e.g., mean, median, standard deviation, range...) will be calculated to summarize quantitative variables such as age, attendance rate, treatment adherence logbook, GAS score, GMFM-88 score and CP QOL-Child score, while frequency distributions and percentages will be used to summarize categorical variables such as gender, GMFCS level (III or IV), socio-economic status, ethnicity, and type of intervention. All that describes the participants' demographic and baseline characteristics, as well as analyses the distribution of the variables of interest.

Statistical analysis will be done to test the hypothesis using appropriate methodologies based on the data distribution and characteristics. For quantitative variables, t-tests or ANOVA may be used to compare means between the two groups (play therapy-based physiotherapy versus conventional physiotherapy). However, for categorical variables, chi-square or Fisher's exact test might be used, but in this study, it may not be necessary as the hypothesis doesn't include categorical variables.

Moreover, linear regression analysis may be used to investigate the association between treatment adherence and gross motor function while to identify predictors of treatment adherence, gross motor function and quality of life, including age, gender, GMFCS level, social-economic status, ethnicity, and treatment group so potential confounding variables will be controlled for in the

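### The protocol counts goal attainment (GAS) as a measure of the primary outcome adherence, so a GAS difference with equal compliance could be reported as better adherence

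*Protocol*

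**What the plan says.** Section 9.4 names "treatment adherence and gross motor function as primary outcome measures and quality of life as a secondary measure". Section 9.4.1 says that adherence "refers to the extent to which a patient follows or complies with the recommended or prescribed treatment plan". The same sentence goes on to describe how treatment is agreed with the family, taking their goals into account.

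The abstract, in both languages, lists three measures: "Treatment adherence will be measured using a combination of physiotherapy session attendance rates, an adherence logbook and the Goal Attainment Scale (GAS". Section 9.4.1 describes the logbook first and then adds GAS, which it describes thus: "method to measure if the goals determined before starting the intervention has been achieved or not (B), which is highly related to treatment adherence". No other reason is given for including it.

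On the goals themselves, section 9.4.1 says "This goal setting will be done based on parents or guardians" and on the child's needs and motivations. Section 9.3 says that control sessions are planned for each child's "needs and goals, for improving gross motor function and increasing treatment adherence"; the play arm is also directed at gross motor function.

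Section 9.5 schedules GAS at baseline and at weeks 5, 10, 16 and 24. It states that "in the mid-term assessments the goals achievement will be measured, all this by the physiotherapist", and Table 2 likewise gives GAS to the physiotherapists. Section 9.1 says that physiotherapists cannot be blinded. The sessions end at week 16, and the logbook is handed over then.

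Section 9.6 and Annex V list attendance rate, logbook and GAS as separate variables, with no rule for combining or ranking them. Section 9.6 adds that "linear regression analysis may be used to investigate the association between treatment adherence and gross motor function", without saying which adherence variable would be used.

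**The concern.** Adherence, as the protocol defines it, is behaviour: whether the child and family do what was prescribed. GAS records whether something was achieved. The two may be correlated, but whether better compliance leads to better results is a question for the trial and should not be built into the measurement.

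Two inferences are exposed. First, specific objectives I (adherence) and II (gross motor function) are meant to be separate claims. If GAS counts as adherence, an arm that reaches more goals with no better compliance could be credited with better adherence. Second, if GAS supplies or contributes to the adherence variable in the section 9.6 regression, and the goals are partly motor, that analysis relates one measure of motor gain to another.

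Scoring by the unblinded treating physiotherapist adds a further route by which GAS could differ between arms while compliance does not. The week-24 score also falls eight weeks after the last session (24 − 16 = 8).

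**Working it through.** **Text.** The definition concerns following a plan; the instrument concerns reaching goals. The definition does mention goals, but only as something settled when treatment is chosen. Setting a goal is not attaining it, so the definition does not cover GAS scores.

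**Design inputs.** 32 per arm (section 9.2.1) and two-sided 0.05 (section 9.6 and Annex I; section 9.2.1 prints 0.5). The Annex I arithmetic reproduces: 2 × 2.43² × (1.96 + 0.8416)² / 1.2² = 64.37. That formula gives a number per arm, which is a separate matter; only the 32 per arm is used below.

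**GAS tested alone, no adherence difference.** For a standardised GAS effect δ, the non-centrality is δ × √(32/2) = 4δ, against a critical t of 2.00 on 62 df.
- δ = 0.3: 4 × 0.3 = 1.20, significant in about 22% of trials.
- δ = 1.2/2.43 = 0.49: 4 × 0.494 = 1.98, significant in about 49%.

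Both effects are assumptions. The 0.49 is borrowed from Annex I, which does not name its outcome and labels 1.2 as already standardised while using it as a raw difference.

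**GAS moved only through motor function.** Suppose a motor effect of m SD and a GAS-motor correlation ρ, so the GAS effect is ρm. Attendance and logbook have no group effect, correlate 0.5 with each other and are unrelated to motor function. None of these values is in the protocol. For an equally weighted mean of the three measures, the variance of the sum is 3 + 2 × 0.5 = 4, so the SD of the mean is 2/3 and the standardised effect is (ρm/3)/(2/3) = ρm/2. Results from 20,000 simulated trials, as the percentage with a significant group difference:

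| Motor effect | ρ | GAS alone | Any of three | Mean of three |
|---|---|---|---|---|
| 0.5 SD | 0.3 | 9% | 17% | 6% |
| 0.5 SD | 0.5 | 16% | 24% | 8% |
| 0.5 SD | 0.7 | 28% | 35% | 11% |
| 0.8 SD | 0.3 | 16% | 24% | 7% |
| 0.8 SD | 0.5 | 35% | 41% | 13% |
| 0.8 SD | 0.7 | 60% | 64% | 20% |

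The benchmark is 5% for GAS alone and for the mean. For the any-of-three reading, the comparison is about 9% when only attendance and logbook are tested.

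**Regression.** Under the same assumptions there is no true link between compliance and motor function. Within groups, the averaged score correlates ρ/2 with motor function (0.15, 0.25, 0.35). The association is significant in 22%, 51% and 81% of trials with the averaged score, and in 67%, 99% and 100% with GAS alone. Without GAS it is 5%, but that figure follows from assuming the logbook unrelated to motor ability.

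**The case against.** The best defence is that GAS never decides adherence. Section 9.6 and Annex V list the three variables separately, and Table 2 names the logbook and GAS as distinct items, so a GAS difference would appear under its own name. Section 9.4.1 introduces GAS as an addition, which can be read as a related extra. The regression is optional, and for predictors of adherence section 9.6 names the parts of the logbook. The choice of adherence variable could properly be left to an analysis plan.

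Much of this stands, and it rules out several stronger readings that a reader might infer:
- That a child with full attendance and every exercise done, but no goal reached, would be scored as poorly adherent. No scoring rule says so; that child would have 100% attendance and full task-completion marks.
- That GAS largely duplicates GMFM-88. The goals come from family and child needs and motivations and are not limited to motor function.
- That the regression is circular as planned. This depends on GAS being used and on the goals being motor, and the protocol fixes neither.
- That the week-24 score will be analysed as adherence, or that nothing is left to adhere to by then. The first is not stated, and the home recommendations have no stated end date.

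The defence does not reach the classification itself. The abstract says that adherence is measured by the three together, and separate listing does not withdraw that label. It leaves GAS free to be tested alone and reported under the adherence objective. An analysis plan could choose the variable, but the protocol has already placed GAS in the adherence construct.

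**Conclusion.** The point holds as a misclassification within a primary outcome: a result of treatment, scored unblinded, is counted as compliance, and nothing in the protocol prevents a GAS difference from being reported as better adherence.

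Its size is conditional. The GAS-only figures of 22% and 49% are the power to detect an assumed real GAS effect. They become false adherence claims only if GAS alone is taken to settle adherence, so it would be wrong to say that the trial carries a 49% false-positive rate for adherence. If GAS is moved only by a 0.5 SD motor effect, the range is about 9% to 28% for GAS alone and 6% to 11% for an averaged score. The direction is the same throughout; the magnitude rests on correlations and effects that the protocol does not give. The problem with the regression arises only if GAS is used there, and only so far as the goals are motor. The GMFM-88 comparison with blinded assessors is unaffected.

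**What to change.** In the abstract, section 9.4.1 and section 9.6, list GAS as a separate secondary outcome, goal attainment, and define primary adherence from attendance and the logbook compliance items. The outcome list in section 9.4 should match.

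State in section 9.6 that GAS is not the adherence variable in the adherence-motor regression. For that regression, prefer attendance and the item on whether parents followed the home recommendations. The task-completion and help items in Annex IV may themselves depend on motor ability, so removing GAS would not by itself separate the two constructs.

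The cost is protocol wording; the same data are collected on the same schedule. The downside is that adherence then rests on two sources instead of three.
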